CRITERIA FOR EVALUATION	Efficacy in each part of the study will be assessed using the ADHD-RS-5, CGI-I, CGI-S and Conners 3-P(S) scales.  Safety in each part of the study will be assessed by evaluating TEAEs, vital signs measurements (including systolic blood pressure, diastolic blood pressure, pulse rate, respiratory rate, and temperature), measurements of weight, and responses on the C-SSRS.
STATISTICAL METHODS	Study Populations:  The Intent-to-Treat Population of each part of the study includes all subjects who are randomized and dispensed study medication at the Baseline visit. The Full Analysis Set of each part of the study includes all subjects who are randomized, take at least one randomized dose of study medication during this trial, and have a valid Baseline and at least one post-Baseline follow-up assessment of the primary outcome measure - ADHD-RS-5 total score. The Safety Population of each part of the study includes all subjects who are randomized and take at least one randomized dose of study medication and during this trial.
	General Considerations:  Randomization will be implemented in a 1:1 ratio using a computer-generated schedule stratified by age (6 to 12, 13 to 17 years old) and part (A, B). Each part of the study will be analyzed separately. Pooled analyses using both parts may also be conducted, if appropriate. Experimental results will be summarized with descriptive statistics and will be presented by treatment group (AEVI-001 or placebo) and overall. Continuous endpoints will be summarized by the number of subjects (n), mean, median, standard deviation (SD), minimum, and maximum. Categorical and count endpoints will be summarized using n and the percentage of subjects in each category.
	All statistical tests will be 2-sided and performed at the 0.05 level of significance. All confidence intervals (CIs) will be 2-sided 95% CIs. All efficacy analyses will be

conducted using the Full Analysis Set; all safety analyses will be conducted using the Safety Set.

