
AEVI-001 was previously administered to 30 adolescents (ages 12-17) with ADHD and disruptive mutations in GRM-network genes as determined by the presence of CNVs to further establish the safety profile and to explore efficacy of AEVI-001 as a treatment for ADHD in this population (Study NFC1-2014). In this study, AEVI-001 was found to be generally safe and well tolerated. Exploratory results on the Vanderbilt Parent Rating Scale and the Clinical Global Impression-Improvement scale (CGI-I) suggested that AEVI-001 may be an effective treatment for ADHD in these adolescents with CNVs in the GRM network genes.

Additionally, in a recently completed study, AEVI-001 or placebo was administered to 97 adolescents (ages 12-17) with ADHD and disruptive mutations in GRM-network genes as determined by the presence of CNVs to assess the efficacy and AEVI-001 compared to placebo (Study MDGN-NFC1-ADHD-201). Although the study did not meet the *a priori* primary efficacy objective, subjects in the AEVI-001 group did show improvement compared to placebo subjects as measured by 3 previously defined response criteria (a reduction from Baseline of ≥30% in the

ADHD-RS-5 Total score; a CGI-I score of 1 (very much improved) or 2 (much improved) relative to Baseline; and a composite criterion that both of the other 2 criteria be met). On each of these criteria, AEVI-001 subjects were statistically significantly better than placebo subjects. AEVI-001 was also generally safe and well tolerated at doses up to 400 mg bid in the population of adolescents enrolled in this study. Post-hoc analyses examined factors such as gene mutations that were predictive of treatment response. The results of these analyses revealed 9 genes associated with robust treatment response in multiple subjects. The genes included certain GRM genes and other CNS/neurodevelopmental genes, e.g., *CNTN4*. The most frequent gene copy number variant in the study population (n=19, 19% of randomized sample) was *CNTN4*. As such, the replication of this finding is the focus of this Phase 2 study.

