### 14. STATISTICS

Each part of the study will be analyzed separately. Pooled analyses using both parts may also be conducted, if appropriate.

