2.2 Study design

This is a 2-part, 6-week, double-blind, dose-optimization, parallel-group study in children and adolescents (ages 6-17 years) with ADHD with and without CNVs in specific genes implicated in glutamatergic signaling and neuronal connectivity (see Figure 1 for the study design of both parts). Only subjects who had genetic testing performed during another Aevi study (i.e., MDGN-NFC1-ADHD-001, MDGN-NFC1-ADHD-101, or AEVI-001-ADHD-002) and who consented to future research were considered for participation in this study. Part A will include subjects determined to have one of 8 specific gene mutation(s) implicated in glutamatergic signaling and neuronal connectivity. Part B will be conducted and will assess subjects who do not have CNVs in any of the 272 specific gene mutation(s) implicated in glutamatergic signaling and neuronal connectivity. The list of excluded mutations includes the 8 gene mutations studied in Part A and an additional 264 mutations identified in an antecedent study. Once subjects are confirmed as eligible for each part of the study, they will be randomized to one of two treatment groups (AEVI-001 or placebo) in a 1:1 ratio. The randomization will be stratified by age (6 to 12, 13 to 17 years old) and part (A, B) with each part of the study analyzed separately.

During both parts of the study, randomized subjects will receive investigational product (IP) at the Baseline Visit (Visit 2; Day 0) and will begin taking IP at a dose of 100 mg twice daily on Day 1, once in the morning upon awakening (between 7:00 AM to 9:00 AM) and once in the mid-afternoon (between 3:00 PM to 5:00 PM). Dosing will be optimized weekly (± 2 days) to 100 mg, 200 mg, or 400 mg twice daily, as appropriate, over the first 4 weeks of treatment (Dose-optimization Period), based on clinical response and tolerability. If the subject tolerates a dose well, the dose will be maintained for an additional 2 weeks (Dose Maintenance Period). Visits during the Dose-optimization and Dose Maintenance Periods are to be conducted every 7 days (± 2 days). Visits conducted after randomization should be scheduled relative to the Baseline Visit (Visit 2). The primary assessments of safety and efficacy will be performed weekly during the 6-week treatment period. A follow-up telephone call will be performed 7 days (± 2 days) after the last dose of IP. The complete Schedule of Events is included in Appendix A.

[figure not shown]

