2.3 Determination of sample size

For Part A of the study, 42 unique subjects are planned to be randomized to yield approximately 34 subjects who provide post-baseline efficacy data on the primary endpoint. Assuming an effect size of 1.0, this number will yield approximately 80% power to detect a significant difference in mean change from baseline for the ADHD-RS-5 total score at Visit 8 (Week 6) between the treatment groups, based on a 2-tailed test with $\alpha = 0.05$ and 1:1 randomization. In Part A of the study, an interim analysis will be performed when approximately 75% of randomized subjects have completed the study. The sample size could be increased to 64 randomized subjects.

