5.3 Primary efficacy analysis

The change from baseline in ADHD-RS-5 total score will be analyzed with mixed model repeated measures (MMRM) methods using the full analysis set. The model will include derived visit (see Section 4.7), age stratum, treatment group, and treatment-by-visit interaction as fixed factors and baseline ADHD-RS-5 total score as a covariate. Robust variance estimates for the fixed effects will be used for testing treatment differences. Within subject variability will be modeled using an unstructured (i.e., TYPE = UN) covariance pattern. In case of convergence problems, a banded Toeplitz (i.e., TYPE = TOEP(5)) structure for the covariance pattern will be used. The comparison of interest will be the difference between the AEVI-001 and placebo treatment groups at Visit 8. Model based point estimates (i.e., least square [LS] means for each treatment group and the treatment difference), 95% confidence interval for the difference, p-value, and effect size will be reported for each derived visit. Effect size will be calculated as the LS mean difference divided by an estimate of the pooled standard deviation.

Similar MMRM methods will be used to test for treatment differences in each CNTN4 CNV subgroup (see Section 4.3.8 for definition of CNTN4 CNV indicator). To control the overall type I error rate for these subgroup comparisons, a hierarchical testing procedure will be used with comparisons of the primary efficacy variable tested in the following fixed sequence:

- Full analysis set
- Full analysis set CNTN4 CNV subgroup
- Full analysis set Non-CNTN4 CNV subgroup

Supportive MMRM analyses of the primary endpoint will also be performed using the PP analysis set.

Descriptive statistics for the ADHD-RS-5 total score and change from baseline in ADHD-RS-5 total score will be presented by treatment group and derived visit. A similar descriptive statistics display will also be presented by CNTN4 CNV indicator and age stratum.

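### The stated focus is replicating that gene mutations, CNTN4 above all, predict response, but SAP 5.3 never estimates the difference in treatment effect between CNTN4 and non-CNTN4 subjects

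*SAP*

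**What the plan says.** Protocol 6.1 describes the preceding adolescent study, which missed its primary objective: "Post-hoc analyses examined factors such as gene mutations that were predictive of treatment response". It reports nine genes associated with robust response, names CNTN4 as the most frequent variant (19 subjects, 19% of those randomized), and concludes: "As such, the replication of this finding is the focus of this Phase 2 study".

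SAP 4.3.8 derives a yes/no CNTN4 indicator. The primary model in SAP 5.3 has visit, age stratum, treatment, treatment-by-visit and baseline score, and no CNTN4 term. The section continues: "Similar MMRM methods will be used to test for treatment differences in each CNTN4 CNV subgroup". The primary variable is tested in a fixed order: full analysis set, CNTN4 subgroup, non-CNTN4 subgroup. Descriptive displays by CNTN4 indicator are also planned.

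On the two parts, Protocol 14 says: "Each part of the study will be analyzed separately. Pooled analyses using both parts may also be conducted, if appropriate". No pooled model is given. SAP 1 covers Part A only and defers Part B to a separate SAP, which is not among the documents.

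**The concern.** Replicating that a gene predicts response requires a comparison of two treatment effects: drug minus placebo in carriers against drug minus placebo in non-carriers. The plan provides two separate tests, each against zero. One being significant and the other not does not show that the effects differ. The second test may have missed only because its subgroup is small or its sample unlucky.

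CNTN4 status occupies two of the three places in the confirmatory sequence, so the subgroup results will be prominent. If the last step misses 0.05 after the first two succeed, the natural summary is that the drug works in CNTN4 carriers and not in the others. That reading could decide which patients are studied next, without any analysis having addressed the question.

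**Working it through.** **Inputs.** Two-sided 0.05 (Protocol synopsis, statistical methods: "All statistical tests will be 2-sided and performed at the 0.05 level of significance"). Allocation: "they will be randomized to one of two treatment groups (AEVI-001 or placebo) in a 1:1 ratio" (SAP 2.2). Part A size: "42 unique subjects are planned to be randomized to yield approximately 34 subjects who provide post-baseline efficacy data on the primary endpoint" (SAP 2.3), hence 17 per arm. Effect: "Assuming an effect size of 1.0, this number will yield approximately 80% power" (SAP 2.3). The CNTN4 share in Part A is not given. The 19% in Protocol 6.1 comes from a study with a different gene selection, so I use about 25% to 75%. Two-sample t-tests at Visit 8 stand in for the MMRM. Arms are taken as equal within subgroups, although randomization is stratified by age and part and not by CNTN4. The interim sample-size rule is not modeled.

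**The plan's own figure.** Power = P(T > t(0.975; 2n−2)), where T is noncentral t with 2n−2 degrees of freedom and noncentrality d·√(n/2). With n = 17 and d = 1.0 this gives 80.7%, which matches the stated 80%.

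**Chance CNTN4-only pattern under one shared effect of 1.0 SD.** The pattern is: full set significant, CNTN4 significant, non-CNTN4 not, all judged in favor of drug. The subgroups are disjoint, so ignoring the full-set step the probability is (CNTN4 power) × (1 − non-CNTN4 power). Requiring the full-set test to succeed first lowers it a little; the last column is simulated (200,000 trials).

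| Per arm, CNTN4 v other | CNTN4 power | Other power | Product | With full-set step |
|---|---|---|---|---|
| 4 v 13 | 0.22 | 0.69 | 0.07 | 5.6% |
| 6 v 11 | 0.35 | 0.61 | 0.14 | 11.9% |
| 8 v 9 | 0.46 | 0.51 | 0.22 | 20.4% |
| 11 v 6 | 0.61 | 0.35 | 0.40 | 37.4% |
| 13 v 4 | 0.69 | 0.22 | 0.53 | 51.0% |

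Among only those trials in which the full set and CNTN4 have both succeeded, non-CNTN4 fails in 36%, 46% and 64% at 6, 8 and 11 carriers per arm.

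**Larger Part A.** If enrollment rises to 64, the same yield gives 64 × 34/42 ≈ 52 evaluable. The rate is 20.9% at 13 v 13 per arm, and runs from 4.1% (6 v 20) to 55.8% (20 v 6). The increase does not remove the problem.

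**No drug effect.** The same pattern occurs in 0.5% to 1.0% of trials for 6 to 11 carriers per arm, because the full-set test comes first.

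**What a direct contrast can deliver.** In SD units, the standard error of the difference between subgroup effects is √(2/n₁ + 2/n₂). At 8 v 9 this is √(2/8 + 2/9) = 0.687, so the 95% half-width is 1.96 × 0.687 ≈ 1.3 SD. Simulated power for a true difference of 1.0 SD is 29% (42% with 52 evaluable). If a CNTN4-specific claim required a significant contrast, the false CNTN4-only rate at 8 v 9 would fall from 20.4% to 1.8%.

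**Parts A and B.** With a common effect of 0.7, power is 0.508 (17 per arm) and 0.800 (33 per arm). Part A only: 0.508 × 0.200 = 10%. Part B only: 0.492 × 0.800 = 39%. With a common effect of 1.0, Part A only is 0.807 × (1 − 0.979) = 1.7%.

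**The case against.** The strongest reply is that no gene-specific inference is planned. The formal objectives are drug versus placebo, the focus sentence stands in the background section, and showing benefit in carriers of the eight genes and then in CNTN4 carriers is a fair replication of benefit in that population. Neither document says that a non-significant non-CNTN4 test means no effect there. This stands as far as it goes: the primary test is unaffected, and the documents contain no commitment to claim CNTN4 specificity. But the finding to be replicated is described as prediction, and no planned analysis addresses prediction.

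Second, SAP 5.3 asks for least squares mean differences, 95% CIs and effect sizes, with similar methods in each subgroup. Because the subgroups are disjoint, a reader could approximate the difference. True, and it shows how little is being asked. What is missing is a prespecified estimate and a rule for interpreting it.

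Third, the contrast is weak in so few subjects. That is correct, and it is why it belongs in the plan as an estimate and not as a further test.

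Two stronger readings are tempting. A reader might infer that the sequence lets chance alone produce gene findings from an inactive drug; the null figures show that it does not. A reader might also infer that chance will often look CNV-specific across the two parts, since exactly one part is significant in about 50% of trials at a common effect of 0.7. Most of that discordance is Part B only, the opposite pattern, and at 1.0 SD Part A only is about 2%. The Part B SAP may also specify a comparison.

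**Conclusion.** The gap is real and confined to the CNTN4 question: the plan has no estimate of whether the treatment effect differs by CNTN4 status, although that is the finding it sets out to replicate. Its consequence arises when the drug works about equally in both subgroups. A chance CNTN4-only pattern then occurs in roughly one trial in five at a near-even split, and in anything from about 6% to 51% over the carrier shares tried.

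That range, and not one headline rate, is the honest size, because the share is unknown. The 36% to 64% figures hold only after the first two tests have succeeded and should not be quoted as per-trial rates. All of this rests on a shared 1.0 SD effect, 34 evaluable subjects and t-tests in place of the MMRM. The fixed sequence does its own job. This is an inexpensive improvement that should be made; it does not threaten the primary analysis.

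**What to change.** In SAP 5.3, add one full-analysis-set MMRM that extends the primary model with CNTN4, treatment-by-CNTN4, CNTN4-by-visit and treatment-by-CNTN4-by-visit terms. Report the Visit 8 difference between the two subgroup treatment effects with its 95% CI, as an estimate and not as a new gate. State that any claim that CNTN4 predicts response rests on this contrast, and not on one subgroup being significant and the other not. Leave the fixed sequence unchanged.

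If Parts A and B are pooled, report the treatment-by-part difference at Visit 8 with its 95% CI in the same way. With 34 and 66 evaluable its standard error is √(4/34 + 4/66) = 0.42 SD, a half-width of about 0.8 SD.

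The cost is a few sentences and one extra model on data already collected, plus a second if the parts are pooled. The wide CNTN4 interval will make a gene-specific claim harder to support, and a null contrast must not be read as proof that genotype is irrelevant. With so few subjects the added terms may not fit under an unstructured covariance, so a simpler structure, such as the banded Toeplitz fallback already in SAP 5.3, should be named in advance.

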5.4 Secondary efficacy analyses

Logistic regression methods will be used for the analysis of the LOCF ADHD-RS-5 response indicator using the full analysis set. The logistic regression model will include terms for age stratum, treatment group, and baseline ADHD-RS-5 total score. The comparison of interest will be the difference between the AEVI-001 and placebo treatment groups at end-of-treatment. Model based point estimates (i.e., odds ratios), 95% confidence intervals, and p-value will be reported.

Similar logistic regression models will be used for the LOCF CGI-I remission, LOCF combined ADHD-RS-5/CGI-I response, and LOCF combined ADHD-RS-5/CGI-I remission indicators using the full analysis set. For the CGI-I response/remission analyses, baseline CGI-S score will be included in the model. For the combined response/remission analyses, baseline ADHD-RS-5 total and CGI-S scores will be included in the model.

MMRM methods similar to those described in Section 5.3 will be used for the analysis of the following change from baseline values: ADHD-RS-5 inattention subscale, ADHD-RS-5 hyperactivity–impulsivity subscale, and CGI-S, Conners 3-P(S) inattention subscale, Conners 3-P(S) hyperactivity–impulsivity subscale, Conners 3-P(S) learning problems subscale, Conners 3-P(S) executive function subscale, Conners 3-P(S) aggression subscale, and Conners 3-P(S) peer relations subscale. For each model, the baseline score of the respective subscale used in the model will be used as a covariate. For the models including Conners 3-P(S) subscale scores, a heterogeneous first order autoregressive (i.e., TYPE = ARH(1)) covariance structure will be used in cases of convergence problems. As with the primary efficacy analysis, the comparison of interest for each model will be the difference between the AEVI-001 and placebo treatment groups at Week 6. Model based point estimates (i.e., LS means for each treatment group and the treatment difference), 95% confidence interval for the difference, p-value, and effect size will be reported for each derived visit.

Subgroup analyses by ADHD subtype (see Section 4.4.1) will be performed for select secondary efficacy variables. No multiplicity correction to the reported p-values will be made for any secondary efficacy analysis. Supportive analyses of secondary efficacy endpoints may be performed using the PP analysis set.

Descriptive statistics for all scores, change from baseline scores, and response/remission indicators will be summarized by treatment group and derived visit. All ADHD-RS-5, CGI, and Conners 3-P(S) data will be listed by subject and visit.

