### **Secondary Efficacy Endpoints**

Descriptive statistics for the CGI-S score and change from baseline in CGI-S score will be presented by treatment group and visit.

Finally, the dichotomized endpoints of response and remission will be presented as the percentage of subjects meeting the response or remission criteria at Visit 8/ET (Week 6/ET). Both will be scored as 1 for Response/Remission and 0 for non-Response/Remission. Response is defined as:

	A $\geq$ 30% reduction from Baseline in ADHD-RS-5 total score.
	Improved on the CGI-I which includes the categories of 1 (very much improved) and 2 (much improved).
	Both a $\geq$ 30% reduction in ADHD-RS-5 total score and improved (1 [very much improved] and 2 [much improved] on the CGI-I.
Remis	sion is defined as follows:
	An ADHD-RS-5 total score ≤18.
	A CGI-I of 1 (very much improved).
	Both an ADHD-RS-5 total score ≤18 and a CGI-I of 1 (very much improved).
Explo	ratory Efficacy Endnoints

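### SAP 5.4 fits unpenalised logistic models to about 34 subjects with no rule for separation: response odds ratios run moderately high, and a remission odds ratio may not be estimable

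*SAP*

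**What the plan says.** SAP 5.4 opens with a logistic model for LOCF ADHD-RS-5 response, with terms for age stratum, treatment and baseline ADHD-RS-5 total score. It continues: "Similar logistic regression models will be used for the LOCF CGI-I remission, LOCF combined ADHD-RS-5/CGI-I response, and LOCF combined ADHD-RS-5/CGI-I remission indicators". The CGI-I response and remission models take baseline CGI-S; the combined endpoints take both baseline scores. Counting treatment, that makes three terms, or four for the combined endpoints. On output: "Model based point estimates (i.e., odds ratios), 95% confidence intervals, and p-value will be reported". The type of test and interval is not named.

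The strictest remission criterion (Protocol, Secondary Efficacy Endpoints) is "Both an ADHD-RS-5 total score ≤18 and a CGI-I of 1 (very much improved"). The documents give no remission rate.

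On size, SAP 2.3 says "42 unique subjects are planned to be randomized to yield approximately 34 subjects who provide post-baseline efficacy data on the primary endpoint", and adds that "The sample size could be increased to 64 randomized subjects" after the interim analysis. The protocol synopsis sets the level: "All statistical tests will be 2-sided and performed at the 0.05 level of significance".

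SAP 5.3 and 5.4 give fallback covariance structures if the repeated-measures models do not converge. The logistic models have no counterpart.

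**The concern.** Maximum-likelihood odds ratios are biased away from 1 in small samples, and more so with more terms per event. With about 17 subjects per arm, the response odds ratios, including the key secondary CGI-I response, would tend to look larger than they are.

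Remission raises a separate problem. If one arm has no remitter, the treatment odds ratio has no finite estimate. The usual Wald p-value then goes to 1 however strong the contrast. With the test unnamed and no fallback written down, the analyst would have to choose a method after seeing the split. Pre-specification is meant to prevent that.

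**Working it through.** **Inputs.** 42 randomised and about 34 analysed (SAP 2.3), so 17 per arm and a loss of 1 - 34/42 = 19%. If 64 are randomised, 64 × 34/42 = 51.8, about 26 per arm. CGI-I improved rates come from the completed adolescent trial MDGN-NFC1-ADHD-201 (Protocol 6.2): 26/46 = 56.5% vs 16/50 = 32.0%. Remission rates are assumed and varied.

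**The plan's own figure.** SAP 2.3: "Assuming an effect size of 1.0, this number will yield approximately 80% power". A two-sample t-test with 17 per arm has noncentrality 1.0 × √(17/2) = 2.92 on 32 degrees of freedom, giving 80.7% power. This reproduces. The documents state no power or precision for the logistic analyses.

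**Response: events per term.** Expected responders are 17 × (0.320 + 0.565) ≈ 15.0. That is 5.0 per term with three terms and 3.8 with four.

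**Response: size of the bias.** Simulations used 1,000 to 2,000 trials per setting at 32.0% vs 56.5%. One set assumed prognostic covariates (log odds ratio 0.5 per SD of each baseline score, 0.3 for age stratum); the other assumed covariates unrelated to outcome.

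| Model, 17 per arm | Prognostic covariates: true OR | ML geometric mean (median) | Firth geometric mean | Unrelated covariates: ML excess, mean (median) |
|---|---|---|---|---|
| 3 terms | 2.94 | 3.49 (3.34) | 2.93 | 19% (12%) |
| 4 terms | 3.10 | 4.31 (3.94) | 3.28 | 23% (16%) |

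With prognostic covariates the excess is 3.49/2.94 = 1.19 (median 1.14) for three terms and 4.31/3.10 = 1.39 (median 1.27) for four. At 26 per arm, three terms give about 8-10%, and four terms about 19% with prognostic covariates.

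**Response: effect on inference.** In the three-term model, power is about 29% for both Wald ML and Firth. With 32% in both arms, Wald rejection is about 5% and there is no bias. Non-estimable fits occur in under 1% of trials.

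**Remission: chance of an empty cell.** P(no remitter in at least one arm) = q0 + q1 - q0·q1, with q = (1 - rate)^n. At 5% vs 30% and n = 17: 0.95^17 = 0.418 and 0.70^17 = 0.002, so 41.9%. Simulated separation also counts separation involving the covariates. In the power columns, separated Wald fits count as non-significant.

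| Assumed rates | Empty cell, 17 per arm | Empty cell, 26 per arm | Simulated separation, 17 per arm | Power, Wald ML | Power, Firth |
|---|---|---|---|---|---|
| 5% vs 30% | 41.9% | 26.4% | 41-43% | 12-14% | 39-44% |
| 10% vs 35% | 16.7% | 6.5% | 18-19% | 22% | 36-39% |
| 20% vs 35% | 2.3% | 0.3% | 2-4% | 11-12% | 14% |

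**What separation does: 5/17 vs 0/17, treatment only.**
- ML: log odds ratio drifts to 21.7 with standard error about 11,700; Wald p = 0.999.
- Unpenalised likelihood ratio: p = 0.005.
- Firth: odds ratio (5.5/12.5)/(0.5/17.5) = 15.4; penalised likelihood-ratio p = 0.017.
- Fisher exact: p = 0.044.

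**Type I error at equal remission rates of 5-10%, 17 per arm.** The unpenalised likelihood-ratio test rejects in about 7-16% of trials, depending on the number of terms and the simulation assumptions. Firth rejects in about 1-3%.

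**The case against.** The case for leaving the plan alone has real force.

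- **Response conclusions do not move.** Power and Wald type I error are the same either way. Sampling error also dwarfs the bias: the crude standard error of the log odds ratio is √(1/5.44 + 1/11.56 + 1/9.605 + 1/7.395) = 0.714, so the 95% interval spans a factor of exp(1.96 × 0.714) ≈ 4 in each direction. This stands. The response gain is in the estimate, not the test.
- **The larger bias is not the key secondary's.** The four-term model is reserved for the combined endpoints. CGI-I response has three terms if age stratum carries over, and two (treatment and CGI-S) in Protocol 14.1.1, where the excess is about 10% (median 6%). This stands.
- **Remission may not be rare.** At 20% vs 35% separation is 2-4% and the methods barely differ. ADHD-RS-5 remission is not in the list of logistic models, and from the entry minimum of 28 it needs only a 10-point fall (36%). This stands, so the risk is stated as a range.
- **Wald is an inference.** SAP 5.4 names no test, and a likelihood-ratio p-value survives separation. That is true, but that test is too liberal at low rates, and the odds ratio stays infinite whichever p-value is used.
- **Nothing would be concealed.** A reader might infer that the plan could bury a 5 vs 0 split. SAP 5.4 also summarises every response and remission indicator descriptively by treatment group and derived visit, so the counts would appear.

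**Conclusion.** The point holds as a cheap improvement to secondary analyses. On the natural reading of SAP 5.4 (unpenalised maximum likelihood), response odds ratios at 32.0% vs 56.5% are overstated by about 12-20% with three terms and about 25-40% with four. The four-term range assumes prognostic covariates; with unrelated ones it is nearer 16-23%. With 64 randomised, the three-term figure falls to about 8-10%.

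For CGI-I remission and combined remission, separation is a rate-dependent risk: about 40-45%, 20% and 2-4% of trials at the three assumed pairs of rates. The documents give no rate with which to choose among them.

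A reader might infer that infinite odds ratios are to be expected, that the key secondary test is invalid, or that false positives are inflated. The documents support none of these: the first needs a low remission rate that they do not state, and the calculations contradict the other two for Wald tests of response. The primary repeated-measures analysis is not touched.

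**What to change.** In SAP 5.4, before database lock and unblinding, state that the response and remission models are fitted by Firth's penalised likelihood, with profile-likelihood 95% intervals and penalised likelihood-ratio p-values. At minimum, apply this to CGI-I remission and combined remission. Name the p-value explicitly rather than leave it to a software default. Report numerator and denominator by arm beside each odds ratio, and say that only counts are reported if neither arm has a remitter.

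The cost is a sentence or two in the SAP and a small programming change, with no new data. The drawbacks are that odds ratios are pulled toward 1, the method is less familiar to readers, and the test is conservative at very low rates (about 1-3% type I error against a nominal 5%).
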